5 DEFINITIONS OF VARIABLES

This section provides the definitions and sources for all variables used in the analyses, including specifications for the derivations.

General recurrent definitions (e.g., study treatment start date, baseline, and EOS date) or unit conversions are described in Section 11.

5.1 Subject disposition

5.1.1 Screened subjects

A subject is considered screened if the subject has signed any informed consent (for the main study or any of the sub-studies) and is assigned a subject number by the interactive response technology (IRT) provider. A screened subject is considered re-screened if a second screening visit date is documented in the electronic Case Report Form (eCRF).

5.1.2 Screening failures

A subject is considered a screening failure, if screened but not randomized into the study (as per the recording in the IRT system). Subjects screened more than once and subsequently randomized are not counted as screening failures.

The reason for not being randomized is documented on the randomization eCRF:

- Failure to meet randomization criteria (“Subject eligible as per inclusion/exclusion criteria?” answered “No”)

OR

- “Subject withdrew consent” or “Other” (Reason provided following “Was the subject randomized?” answered with “No”)

If a subject at a screening attempt is not randomized but no reason for not being randomized is reported, the reason is categorized as ‘Unknown’. Two variables are derived to hold reason(s) for not being randomized:

- Reason for not being randomized at first attempt (not applicable [NAP], if subject randomized at first attempt; reason derived from first attempt, irrespective of existence and outcome of a second attempt)
- Reason for screening failure (NAP, if subject randomized; reason derived from first attempt if no second attempt, or from second attempt otherwise)

5.1.3 Subjects randomized

A subject is considered randomized if a randomization date and number are recorded in the IRT system.

5.1.4 Subjects treated

A subject is considered treated if they received as least one dose of study drug as documented in any study drug log eCRFs (see Section 5.3.1 for eCRFs involved).

5.1.5 Subject study treatment completion status

Subjects who complete study treatment as per protocol are those with a record in the eCRF ‘Maintenance Ponesimod/Teriflunomide’ form with reason for treatment end given as ‘Completed as per protocol’.

A subject is considered to have prematurely discontinued from the study treatment if:

- at least one reason (‘Study treatment stopped due to’) is reported on the eCRF form ‘Premature Discontinuation of Study Treatment’ and/or
- the reason for treatment end is documented as ‘Premature Permanent Discontinuation’ on the eCRF ‘Up-titration Ponesimod/Placebo’, ‘Up-titration Teriflunomide/Placebo’ or ‘Maintenance Ponesimod/Teriflunomide’

The date of treatment discontinuation is the last date study drug was taken [defined in Section 5.3.1]. In case of a (partially) missing discontinuation date, the date is imputed with the EOS date as defined in Section 5.1.6, or with the upper limit of the partial date if prior to EOS.

Reasons for premature discontinuation from study treatment are documented on the 'Premature Discontinuation of Study Treatment' eCRF with the following possible answers: 'Death', 'Lost to follow-up', 'Pre-specified study treatment discontinuation criteria', 'Subject decision' (further split into 'Tolerability related', 'Efficacy related', 'Other', or 'Not known'), 'Physician decision' (further split into 'Adverse event', 'Lack of efficacy / Treatment failure' or 'Other') or 'Sponsor decision' (further split into 'Study termination by sponsor' or 'Other'). Whenever 'Other' is selected, free text can be provided in addition. Both recorded levels for treatment discontinuation (e.g., 'Subject decision' as well as 'Tolerability related'), if pre-specified, are to be included in analyses, while any free text is not to be reported in tables, only listed. An additional category called 'Reason not provided' is defined for subjects where the reason is missing.

Subjects who have prematurely discontinued treatment are considered to have stayed in the study beyond safety follow-up if their EOS date is after EOT + 30 days. These subjects will be considered to have entered the PTOp beyond the safety follow-up period.

5.1.6 Subject study completion status

A subject is considered to have completed the study as per the corresponding entry on the 'End of Study' eCRF ("Did the subject complete the study?" answered with "Yes"). All subjects not completing the study are considered to have prematurely discontinued the study.

Note: A subject who prematurely discontinued study treatment but completed the PTOp is considered to have completed the study according to the protocol.

The End-of-Study (EOS) date is defined as the 'Date of End of Study' collected on the end of study eCRF, unless a subject is lost to follow-up or dies, in which case 'Date of Last Contact' from the end-of-study eCRF or 'Date of Death' from Death eCRF are used. If missing, the last recorded visit date (i.e., the latest assessment date within any visit) is considered as the EOS date.

For subjects completing the 108 weeks of treatment and entering the extension study, the EOS visit should occur at the FU1 visit (scheduled 14–22 days after last drug intake), or at the abbreviated FU2 visit if available (scheduled 23–37 days after last drug intake). For subjects completing the 108 weeks of treatment and not entering the extension study, the EOS visit corresponds to the FU2 visit (scheduled 30–37 days after last drug intake). For subjects prematurely discontinuing study treatment, EOS is scheduled to be the Week 108 visit (Visit 14A – W108A – Week 108).

For subjects prematurely discontinuing the study, reasons for premature discontinuation from study are: ‘Death’, ‘Lost to follow-up’, ‘Subject decision’ (further split into ‘Withdrawal of consent’, ‘Tolerability related’, ‘Efficacy related’, and ‘Other’), ‘Physician decision’ (further split into ‘Adverse event’ and ‘Other’) or ‘Sponsor decision’ (further split into ‘Study terminated’ and ‘Other’). Whenever ‘Other’ is selected, free text can be provided in addition. An additional category ‘Reason not provided’ is defined for subjects where the reason is missing.

5.1.7 Time in study and time on treatment

Time in study (years) is derived as $(\text{EOS date} - \text{randomization date} + 1 \text{ day}) / 365.25$.

Time in study separated into prior and after protocol version 4 is derived as:

- Time in study after protocol version 4 (years) = $(\text{EOS date} - \text{maximum of (randomization date, start date under protocol version 4)} + 1 \text{ day}) / 365.25$
- Time in study prior to protocol version 4 (years) = Time on study (years) – Time on study after protocol version 4 (years). It is zero for subjects with no data collected under protocol version < 4.

Time on treatment is derived as $(\text{EOT date} - \text{study treatment start date} + 1 \text{ day}) / 365.25$.

5.1.8 Disposition by protocol version

As part of protocol version 4, systematic relapse assessment questionnaires at phone interviews and visits have been introduced, which may affect data collection of the primary endpoint. For each subject, it is therefore established whether they were randomized or had data collected under protocol version 1-3 or under protocol version 4 or higher.

- **Randomized under protocol version (1–3, ≥ 4).** A subject is considered randomized under protocol version ≥ 4 if randomized on or after the start date under protocol version ≥ 4 , otherwise they are considered randomized under protocol version 1–3. The **start date under protocol version 4** is the earliest date of informed consent for the main study on any protocol version > 3 (as documented on the ‘Informed Consent’ eCRF).
- **Data collected under protocol version 1–3 (yes/no).** A subject has data collected under protocol version 1–3 if they have been randomized under protocol version 1–3.
- **Data collected under protocol version ≥ 4 (yes/no).** A subject has data collected under protocol version ≥ 4 if their EOS date is after their start date under protocol version ≥ 4 .

Note: Subjects can have data collected under multiple versions and can have data collected according to both definitions above.

5.2 Subject characteristics

5.2.1 Demographics

The following demographic variables are derived:

- Sex, from the ‘Demographics’ eCRF (Male, Female)
- Age (years), from the ‘Demographics’ eCRF; if available, ‘Age at re-screening’ overwrites the initially entered ‘Age’
- Age categories derived from the above as follows: < 18, 18–30, 31–40, 41–55, and ≥ 56 years. Age high-level categories: < 40, and ≥ 40. Age categories as per EudraCT requirement: < 12, 12–17, 18–64, 65–84, and ≥ 85
- Height (cm), from the ‘Height & Body Weight’ eCRF
- Weight (kg), from the ‘Height & Body Weight’ or from the ‘Body Weight’ eCRF:

The latest measurement available prior to study treatment start date is selected. If first intake is not documented, use the latest measurement available prior to randomization. If neither date is available (for screen failures), the latest weight assessment available is used.

- BMI (kg/m^2) derived as $\text{Weight (kg)} / (\text{Height (cm)} / 100)^2$
- BMI categories: < 18.5, ≥ 18.5 – < 25, ≥ 25 – < 30, and ≥ 30
- Race, from the ‘Demographics’ eCRF (Black or African American, American Indian or Alaska Native, Asian, Native Hawaiian or Other Pacific Islander, White, Other, and Not applicable)
- Ethnicity, from the ‘Demographics’ eCRF (Hispanic or Latino, Not Hispanic or Latino, and Unknown)
- Country based on site mapping performed on SDTM level
- Geographical region of site, countries are assigned to the following regions:
 - European Union (EU): Bulgaria, Croatia, Czech Republic, Finland, France, Germany, Greece, Hungary, Italy, Latvia, Lithuania, Poland, Portugal, Romania, Spain, Sweden, United Kingdom
 - Europe Non-EU + Russia: Belarus, Bosnia and Herzegovina, Georgia, Russian Federation, Serbia, Ukraine
 - North America: Canada, United States
 - Rest of World: Israel, Mexico, Turkey

5.2.2 Baseline disease characteristics

Baseline characteristics variables are defined as follows:

Stratification variables from IRT

- **Baseline expanded disability status scale (EDSS) (from IRT)** (≤ 3.5 , > 3.5) from the IRT system
- **MS disease modifying treatment within 2 years prior to randomization (from IRT)** (Yes/No), from IRT system

Baseline disease characteristics variables from eCRF / non-IRT external data

- **Baseline EDSS score**, defined as the latest available EDSS score as entered in the EDSS/FS eCRF (i.e., not re-derived based on sub-scores) prior to or on the date of randomization
- **Baseline EDSS (from eCRF)**, categorized as (≤ 3.5 , > 3.5), derived from the baseline EDSS score
- **MS disease modifying treatment within 2 years prior to randomization (from eCRF)** (Yes/No), each documented Disease modifying therapies for MS (DMTs), as specified in Section 5.2.5.4, will be flagged as follows:

‘Taken in previous 2 years’, if:

- Medication end date* is after/on randomization date – 730 days and prior to randomization date; or
- Medication end date* is after/on randomization date – 730 days and start date* is not after date of randomization; or
- Medication start date* is after/on randomization date – 730 days and prior to randomization date; or
- Ongoing at end of study? is ticked “Yes” and start date* is available and not after date of randomization; or
- Ongoing at start of Treatment? is ticked “Yes”, unless end date* is prior to randomization date – 730 days.

‘Not taken in previous 2 years’, if

- Medication end date* is prior to randomization date – 730 days; or
- Medication start date* of the medication is after the randomization date.

‘Undetermined whether taken in previous 2 years’, if

- Medication end date is partial and only part of its range[^] is within the period between randomization date – 730 days and randomization date; or
- Medication end date is missing but question “Ongoing at start of Treatment?” is not ticked “Yes” and either start date* is prior to randomization date – 730 days, or start date is missing.

*Or in case of partial dates if the entire range[^] of possible dates (both lower and upper limit) falls within the specified period.

^ Range of partial dates is the time interval defined by lower and upper limit of the partial date.

A subject is considered as having had **MS disease modifying treatment within 2 years prior to randomization (from eCRF)**, if they either have at least one DMT flagged ‘Taken in previous 2 years’, or if they have any DMT flagged as ‘Undetermined whether taken in previous 2 years’ and the site classified the subject for ‘MS treatment within 2 years (from IRT)’ as ‘Yes’. All other subjects are not considered to have had DMT in the last two years prior to randomization.

Any prior MS disease modifying treatment (Yes/No), any DMT prior to randomization, i.e., classified as previous, or ongoing at study treatment start (derived as specified in Section 5.2.5, or ongoing at randomization for non-treated randomized subjects), unless the start date is between randomization date + 1 and study treatment start date.

- **Time since first symptoms (years)**, defined as [Date of randomization – Date of first MS symptoms + 1] in days / 365.25. Taken from ‘MS History Disease Characteristics’ eCRF at screening. Partial dates of first MS symptoms are imputed to the 1st day of the month (if the day is missing) and to the 1st of January (if the day and month are missing). No imputation is performed if the date is completely missing.
- **Time since initial diagnosis (years)**, defined as: [Date of randomization – Date of initial diagnosis + 1] in days / 365.25. Taken from ‘MS History Disease Characteristics’ eCRF at screening. Partial dates of initial diagnosis are imputed to the maximum of [Date of first MS symptoms, 1st day of the month] (if the day is missing) and to the maximum of [Date of first MS symptoms, 1st of January] (if the day and month are missing). No imputation is performed if the date is completely missing.
- **MS subtype (RRMS / SPMS)**, relapsing-remitting multiple sclerosis [RRMS], secondary progressive multiple sclerosis [SPMS] with superimposed relapses). Taken from ‘MS History Disease Characteristics’ eCRF at screening; subtype at re-screening overwrites the initially entered subtype.
- **Time since most recent relapse (months) at screening**, defined as [Date of screening – Onset date of latest MS relapse prior to screening + 1] in days / 30.4375. From eCRF form ‘MS History - Relapse’ at screening. Take the most recent “Onset date of previous relapse” among all previous relapses entered on the ‘MS History - Relapse’ eCRF. Partial onset dates are imputed to the maximum of [Date of first MS symptoms, 1st day of the month] (if the day is missing) and to the maximum of [Date of first MS symptoms, 1st of January] (if the day and month are missing). Data collected at re-screening overwrites the initially entered data.

- **Number of relapses in the year prior to study entry**, as reported in the corresponding question on the ‘MS History - Relapse’ eCRF (i.e., not based on recorded onset dates of previous relapses). Data collected at re-screening overwrites the initially entered data.
 - **Number of relapses in the 2 years prior to study entry** as reported in the corresponding question on the ‘MS History - Relapse’ eCRF (i.e., not based on recorded onset dates of previous relapses). Data collected at re-screening overwrites the initially entered data.
 - **Presence of Gd+ T1 lesions (yes/no)** on baseline MRI scan as provided by the MRI central reading.
 - **Number of documented Gd+ T1 lesions** on baseline MRI scan as provided by the MRI central reading.
 - **Volume of T2 lesions** on baseline MRI scan as provided by the MRI central reading.
 - **Number of T2 lesions** on baseline MRI scan as provided by the MRI central reading, categorized into < 9 and ≥ 9 .
 - **Highly active disease (yes, no)**. A subject is considered to have highly active disease if one or both of the following conditions are met:
 - Any disease modifying therapy for MS as specified in Section 5.2.5.4 received during the year* before randomization and one or both of the following conditions are met:
 - ≥ 1 relapse within 1 year prior to study entry and the baseline MRI read centrally shows either ≥ 1 Gd+ T1 lesion and/or ≥ 9 T2 lesions
 - Number of relapses within 1 year prior to study entry \geq number of relapses between 2 and 1 year prior to study entry, for subjects with at least one relapse within 2 years prior to study entry.
 - ≥ 2 relapses within the 1 year prior to study entry and baseline EDSS score > 2 and baseline MRI read centrally shows ≥ 1 Gd+ T1 lesion.
- * i.e., any intake documented between randomization date – 365 days and randomization date; (partially) missing medication start and stop dates are imputed as described in Section 12.1.
- A subject is considered not to have a highly active disease if either condition stated above is not met unless either condition cannot be assessed due to missing data.
- **Smoking status** (Current smoker, Former smoker, Never smoked), taken from ‘Smoking status’ eCRF.

Note: For re-screened subjects, information for baseline characteristics 'at screening' is taken from the last Re-screening Visit, if available, instead of the Screening Visit.

Handling of missing/partial dates: In case of partial dates for required dates (MS symptoms, initial diagnosis, latest MS relapse prior to Screening), the lower limit is used in derivations. Missing dates are not replaced; the corresponding variable is considered missing.

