8 DEFINITION OF SUBGROUPS

The below described subgroups are considered in selected efficacy analyses. If applicable, the category in bold type is the reference category used in the statistical analysis of these subgroups.

- Prior use of MS disease-modifying treatment in the last two years prior to randomization (yes, **no**) as documented by the IRT system and used as randomization strata.
- Baseline Expanded Disability Status Scale score (**EDSS ≤ 3.5**, EDSS > 3.5) as documented by the IRT system and used as randomization strata.
- Prior use of MS disease-modifying treatment in the last two years prior to randomization (yes, **no**) as derived based on medications entered in the eCRF [see Section 5.2.2].
- Any prior treatment for MS (yes, **no**).
- Baseline Expanded Disability Status Scale score (**EDSS ≤ 3.5**, EDSS > 3.5) as documented in the eCRF.
- Geographical region of site (Europe Non-EU + Russia, European Union (EU) + UK, North America, Rest of World), as defined in Section 5.2.1;
- Sex (**male**, female);
- Age at screening (< **40 years**, ≥ 40 years);
- MS subtype (**relapsing remitting**, secondary progressive with superimposed relapses)

- Number of documented MS relapses within the last 12 months prior to screening (≤ 1 , ≥ 2), as defined in Section 5.2.2;
- Gd+ T1 lesions at baseline, on MRI scan as provided by the central reader (**absent**, **present**);
- Highly active disease (yes, **no**), as defined in Section 5.2.2;
- Protocol version at randomization:
 - **Randomized pre-PV4**: Subjects who have consented originally to protocol versions 1 to 3; these subjects can have data collected under protocol versions 1 to 3 only or under protocol versions 1 to 4.
 - **Randomized post-PV4**: Subjects who have consented to PV4 only; data of these subjects is only being collected under PV4.derived as described in Section 5.1.8.

In case of missing information, the corresponding subject is not considered for the respective subgroup analysis.

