9.6.7 Subgroup analyses

Subgroup analyses for confirmed relapses up to EOS will be conducted on the subgroup variables listed in Section [8](#) using the FAS and will be repeated for a Per Protocol analysis. The analysis is conducted to assess consistency of the overall treatment effect across subgroup variables.

A separate NB model will be fitted within each subgroup level for confirmed relapses up to EOS, with treatment as the only covariate and the log of the time (in years) from randomization up to EOS as an offset variable. Estimates of ARR by treatment arm, rate ratio with 99% CIs within each subgroup level will be presented, accompanied by the number of subjects per category. The analysis is repeated presenting 95% CIs within each subgroup level.

The treatment-by-subgroup interaction p-value is estimated for each subgroup variable from a separate model including treatment, the subgroup and the treatment-by-subgroup interaction term(s) using a Likelihood ratio test. Interactions with a p-value < 0.01 will be investigated further to determine the nature of the interaction (quantitative or qualitative) and the association with other subgroups.

Results are presented in a summary table and in a forest plot. The forest plot will include the 'overall' treatment effect, based on the primary efficacy analysis as a reference line. Point estimates are presented within the forest plot with its size proportional to the number of subjects in the subgroup.

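### SAP Section 5.2.2 gives two non-complementary rules for highly active disease, so a fully assessed subject meeting exactly one condition is both yes and no

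*SAP*

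**What the plan says.** Section 5.2.2 defines a binary baseline variable for highly active disease. The affirmative rule is: "A subject is considered to have highly active disease if one or both of the following conditions are met".

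- **Condition 1** needs a DMT "received during the year* before randomization and one or both of the following conditions are met". The first sub-route is at least one relapse in the prior year with a baseline MRI showing at least one Gd+ T1 lesion or at least nine T2 lesions. The second compares relapse counts between the last year and the year before it.
- **Condition 2** does not mention DMT. It requires at least two "relapses within the 1 year prior to study entry and baseline EDSS score" above 2, together with at least one Gd+ T1 lesion at baseline.

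The negative rule follows: "A subject is considered not to have a highly active disease if either condition stated above is not met". It carries an exception: "unless either condition cannot be assessed due to missing data".

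Section 8 lists the variable as a subgroup, "Highly active disease (yes, no), as defined in Section 5.2.2", with *no* as the reference level. It also says how missing status is handled: "In case of missing information, the corresponding subject is not considered for the respective subgroup analysis".

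**The concern.** The affirmative rule is condition 1 OR condition 2. Its complement is that neither condition is met. The negative rule as worded is NOT condition 1 OR NOT condition 2, which is the complement of meeting both. A subject with exactly one condition therefore satisfies both rules, and the SAP gives no order of precedence.

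The two conditions describe alternative routes, one of them open only to subjects with a recent DMT, so meeting exactly one is not an edge case. The classification then depends on which sentence the programmer implements, or implements last.

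The variable is tabulated at baseline (Section 9.4.2). For the primary endpoint, Section 9.6.7 says: "Subgroup analyses for confirmed relapses up to EOS will be conducted on the subgroup variables listed in Section" 8. That analysis is repeated per protocol and includes an interaction test, with further investigation if p < 0.01. The same subgroup list is used for fatigue, CUAL, 12-week CDA and 24-week CDA. One misreading would move the same subjects into the reference level in all of these outputs.

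**Working it through.** The SAP states no figure to reproduce, so the check is logical first and then illustrative.

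**1. Truth table.** Each condition can be met, not met or not assessable, giving nine cells. The last column reads *no* as neither condition met.

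| Condition 1 | Condition 2 | Both sentences as written | Negative sentence overrides | *No* = neither met |
|---|---|---|---|---|
| met | met | yes | yes | yes |
| met | not met | **yes and no** | no | yes |
| not met | met | **yes and no** | no | yes |
| not met | not met | no | no | no |
| met | not assessable | yes | yes | yes |
| not assessable | met | yes | yes | yes |
| not met | not assessable | missing | missing | missing |
| not assessable | not met | missing | missing | missing |
| not assessable | not assessable | missing | missing | missing |

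Two of the nine cells conflict. With the neither reading every cell has exactly one status: five yes, one no, three missing.

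**2. What happens to condition 2.** A subject with no DMT in the prior year fails condition 1 by definition. If the negative sentence governs, that subject is *no* whatever the relapse count, EDSS or MRI. Conversely, a subject who meets condition 2 and did take a DMT in that year also meets condition 1 through its first sub-route, since two relapses imply one and one Gd+ lesion is enough. So fully assessed subjects who meet only condition 2 are exactly those without a recent DMT, and an overriding negative sentence would remove all of them. Condition 2 would stop being an alternative route and become an extra requirement.

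**3. Illustrative size.** The SAP gives N = 1133 (Section 2) and no prevalence for either condition. The shares below and their independence are assumptions. With p1 and p2 the shares meeting each condition:

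- at least one = N × (p1 + p2 − p1·p2)
- both = N × p1·p2
- exactly one = N × (p1 + p2 − 2·p1·p2)

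| p1 | p2 | At least one | Both | Exactly one |
|---|---|---|---|---|
| 10% | 5% | 164 | 6 | 159 |
| 10% | 20% | 317 | 23 | 295 |
| 40% | 5% | 487 | 23 | 465 |
| 40% | 20% | 589 | 91 | 499 |

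Lower corner: 1133 × (0.10 + 0.05 − 0.01) = 1133 × 0.14 = 159. Upper corner: 1133 × (0.40 + 0.20 − 0.16) = 1133 × 0.44 = 499. The exactly-one share rises in both p1 and p2 over this range, so these corners are the extremes.

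By step 2, independence here means that the share of condition-2 subjects with a recent DMT equals p1. A larger share would lower the exactly-one count; a smaller share would raise it.

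**The case against.** The best defence is that the intent can be recovered. The affirmative definition comes first and says that one condition is enough; letting the negative sentence override it would make that wording pointless and disable condition 2 for subjects without a recent DMT. The missing-data exception points the same way: if failing one condition were enough for *no*, it would not matter that the other could not be assessed. The wording was most likely meant as neither condition met, and a careful programmer may implement it so. This stands, and it limits how serious the point is. It does not remove the contradiction, because correct classification then depends on someone overriding a written sentence.

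Three stronger readings are tempting and are not supported:

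- A reader might infer that the text as written empties the *yes* group of everyone who does not meet both conditions. It does not. The two sentences together give both labels, and the group shrinks only if the negative one takes precedence, which the SAP nowhere says. Even then, a subject who meets one condition and cannot be assessed on the other stays *yes*.
- A reader might infer that the missing-data exception has the same flaw and loses subjects who meet one condition. It only blocks the assignment of *no*; the affirmative sentence still makes them *yes*.
- A reader might infer that confirmatory results are at risk. The variable is not in the primary model (Section 9.6.3), and Section 9.1.1 treats tests outside the primary and secondary strategy as exploratory.

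**Conclusion.** The definition is wrong as written and should be corrected. The two sentences assign mutually exclusive values to every fully assessed subject who meets exactly one condition, with no precedence between them. If the negative sentence were programmed or applied last, the *yes* group among fully assessed subjects would fall from those meeting at least one condition to those meeting both.

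The number affected cannot be computed from the SAP. Under the assumed ranges and independence it is roughly 160 to 500 of 1133, against about 6 to 91 meeting both. That shows the possible scale under one reading and is not an estimate for this trial.

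The consequence is confined to the baseline table and to the subgroup analyses of the primary and secondary endpoints. The primary test, the confirmatory secondary tests and type I error control are unaffected.

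**What to change.** Replace the negative sentence in Section 5.2.2 with a rule to this effect: highly active disease is *no* when neither of the two conditions is met, and status is missing only when no condition is met and at least one cannot be assessed because of missing data. The affirmative sentence stays as it is. Each of the nine combinations then has exactly one status, and it is explicit that one met condition is enough even if the other cannot be assessed. That matters because Section 8 drops subjects with missing status from the subgroup analysis.

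The cost is one sentence in the SAP and a check that the derivation program follows it, ideally before unblinding. No new data, analysis or sample size change is needed.
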